6 STUDY TREATMENT

6.1 Investigational Product(s)

Y14 is a 35 amino acid linear peptide. Y14 does not contain any products of human or animal origin.

The bulk drug product (20 mg/vial) is manufactured as a 2 mL ISO clear Type 1 tubular glass vial with a 13mm crimp neck. The vials are sealed with a fluoro-coated lyophilisation stopper and an aluminium crimp seal. Y14 will be reconstituted in sterile diluent supplied in a glass vial with a fluoro-coated rubber stopper and an aluminium crimp seal. The details of the diluent and reconstitution steps will be provided in the IMP Preparation Information.

The placebo is sterile 0.9% (w/v) saline.

6.1.1 Supply, Packaging and Labelling

Y14 bulk Drug Product and Diluent will be supplied to Covance Clinical Research Unit by AMRI (Glasgow).

A release document signed by a legally authorised Qualified Person (QP) at Covance Clinical Research Unit will be placed in the appropriate section of the Trial Master File to document labelling and dispensing of the study drug to the subject. A technical agreement between Covance Clinical Research Unit and Sponsor will be in place to cover all pharmacy related activities, detailing roles and responsibilities prior to receipt of the IMPs at Covance Clinical Research Unit.

These supplies will be packaged in accordance with Annex 13 of “The Rules Governing Medicinal Products in European Community, Volume IV Good Manufacturing Practice for Medicinal Products”.

All documents required to perform GMP activities at Covance Clinical Research Unit will be supplied as per the Technical Agreement. The Technical Agreement will outline the roles and responsibilities between the contract giver and the contract acceptor.

The placebo (sterile 0.9% [w/v] saline) will be commercially sourced by Covance Clinical Research Unit.

6.1.2 Storage and Handling Procedures

The Y14 lyophilised powder will be stored at -15 to -25°C. The diluent will be stored at +2 to +8°C. All study medication will be stored in the CRO Pharmacy.

Details of how the IMP will be prepared for administration will be included in a separate IMP Preparation Information document.

The Sponsor will be permitted upon request to audit the supplies, storage, dispensing procedures and records provided that the blind of the study is not compromised.

CONFIDENTIAL**6.1.3 Accountability**

In accordance with GCP, the clinical unit will account for all supplies of Y14 and placebo. Details of receipt, storage, assembly and return will be recorded.

All unused supplies of Y14 and placebo will either be destroyed by CRO or returned to the study Sponsor at the end of the study in accordance with instructions by the Sponsor.

6.2 Dosage and Administration

Y14 or placebo will be administered by SC injection into the abdomen. The maximum individual injection volume will not exceed 1.0 mL, though multiple injections (up to 5) may be given for a single dose. The injection site(s) should be circled with indelible marker (or the position recorded in some other suitable manner) and inspected at each AE check during Day 1. Reactions should be described according to the grading table (Table 7.4). Where multiple doses of Y14 are given to the volunteer, the injection sites must rotate, i.e. given at different sites in the abdomen.

In the event of injection site reactions thought to be related to the volume of the injection, the dose of Y14 or placebo may be fractionated and up to 5 injections may be given.

Subjects will receive Y14 or placebo, whilst in the supine/semi-supine position, said dose to be given 1 hour after the subject has completed eating a standardised breakfast. Subjects will remain confined to their beds for a period of 4 h after injection, but will be permitted to visit the bathroom to use the toilet if needed.

In Part A (SAD) the proposed doses are: 1 mg, 4 mg, 8 mg, 16 mg, 32 mg, 64 mg and 96 mg. Depending on emerging safety, tolerability and PK data, the doses given may be modified. Dose levels administered in Part B (MAD) will be selected following review of the data from Part A. In Part B, dose titration for an individual subject may be necessary within a dosing regimen depending on the activity profile and tolerability, but will not exceed the maximum dose tested in the SAD trial.

Subjects will not eat for 4 h postdose after which time lunch will be served. Dinner will be served 10 h postdose.

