It was also observed in the Y242 study that skin reactions were a common TEAE. Dose levels or concentrations may require adjustment accordingly, and the initial doses given during the SAD phase of the study will be limited to 20 mg/ml. If necessary, the doses may be divided into multiple injections to reduce injection volumes and the amount of Y14 administered per injection site. In addition local tolerance and in particular injection site reactions will be monitored closely throughout the study.

PYY is known to cause a 30% increase in urinary sodium output when given to healthy human volunteers, but no significant change in urinary volumes [21]. In the Y242 trial, a natriuretic

CONFIDENTIAL

Synoptic Clinical Study Protocol
Version 2.0 - 05/08/2017

EudraCT Number: 2017-000380-33

effect was not observed. In the target clinical population of obese people, hypertension is a common co-morbidity, and it is anticipated that, if Y14 does indeed cause a natriuresis, this may ameliorate hypertension [21]. GLP-1 has a similar natriuretic effect in humans [22] and this effect is thought to underlie its anti-hypertensive action [23].

No other safety concerns are anticipated, but monitoring of an extensive list of safety variables will take place during this study.

The proposed study is a single and double-blind, randomised, placebo controlled Phase I FIH study to be conducted in 2 parts (Parts A and B);

As this is a FIH study a sentinel dosing strategy will be used for the first dosing group. Safety data up to and including 24 h postdose will be reviewed by the Investigator prior to dosing the remaining subjects at that dose level 48 h later. Dose escalation will only occur if the previous dose level was deemed to be safe and well tolerated.

Part B will only commence after appropriate and sufficient data from Part A are available to enable the determination of a safe starting dose for Part B. Administration of subsequent dose levels will be based on review of available safety, tolerability and PK data from previous doses. As with Part A, progression to the next higher dose will only occur if the previous dose level was deemed to be safe and well tolerated. In Part B, dose titration for an individual subject may be necessary within a dosing regimen depending on the activity profile and tolerability.

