5.1.2 Part B (Multiple Ascending Dose)

Part B will be a double blind, randomised, placebo controlled, multiple ascending dose (MAD) study in sequential groups of male subjects (BMI range 25-38 kg/m²). These subjects can either have normal glucose tolerance, prediabetes (impaired glucose tolerance or impaired fasting glucose) or Type 2 diabetes, defined according to WHO 2006 and 2011 diagnostic criteria. If the subject is diagnosed with diabetes or prediabetes, this condition should be stably controlled either with:

- i. diet only;
- ii. monotherapy with a sulphonylurea, metformin, or SGLT-2 inhibitor;
- iii. dual therapy with a sulphonylurea, metformin, and/or a SGLT-2 inhibitor;
- iv. or triple therapy with a sulphonylurea, metformin, and SGLT-2 inhibitor.

Patients treated with other anti-diabetic treatments are excluded.

Where subjects have prediabetes or diabetes, their HbA1c at screening should be 6.0–8.5% (42–69 mmol/mol) and <±1.0% (±11 mmol/mol) from a previous HbA1c reading within the last 6 months, where available. Where a HbA1c reading within the last 6 months is not available, the subject should have HbA1c re-measured after at least 4 weeks to assure stability of glycaemia before inclusion in the study. This remeasurement may take place any time up to and including check in on Day -2.

For other subjects without known diabetes or pre-diabetes, or in whom the glycaemic status is in doubt, they may attend a pre-screening visit no more than 10 weeks before Day 1, where a fasting glucose and HbA1c will be measured, and a 75 g oral glucose tolerance test performed to classify their diagnosis according to the WHO 2006 and 2011 criteria.

It is proposed to investigate 3 dose levels of Y14 in up to 3 cohorts of 8 subjects, anticipated total of 24 subjects. In each cohort 6 subjects will receive Y14 and 2 subjects will receive placebo. Where possible, subjects of a similar glycaemic status (i.e. diabetics, prediabetics or normal glucose tolerance) will be grouped in a cohort.

Up to 3 additional cohorts of 8 patients each, i.e. up to 24 subjects in addition, may be enrolled if recommended by the Safety Committee (see Section 7.1.4) to increase scientific value of this study, e.g. to assess additional doses of Y14 or further characterise PD markers.

Part B may commence prior to the completion of Part A (SAD) and the total daily dose will not exceed a single dose shown to be safe and well tolerated.

CONFIDENTIAL

Synoptic Clinical Study Protocol

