Version 2.0 - 05/08/2017

EudraCT Number: 2017-000380-33

Subjects will receive 5 doses of Y14 or placebo by SC injection (with fractionation if needed), each separated by 7 days (i.e., on Days 1, 8, 15, 22, 29). The starting dose level to be administered in Part B will be determined from Part A. Administration of subsequent doses will be based on review of available data on safety, tolerability and PK up to 48 hours after the last dose, gathered from previous doses in a minimum of 6 subjects. The individual doses to be given in Part B will not exceed the maximal tolerable dose identified from Part A. Dose titration for an individual subject may be necessary within a dosing regimen depending on the activity profile and tolerability.

[figure not shown]
Subjects are proposed to have 6 inpatient stays in Part B as outlined in Figure 5.1.

CONFIDENTIAL

Synoptic Clinical Study Protocol
Version 2.0 - 05/08/2017

EudraCT Number: 2017-000380-33

Figure 5.1 Study Overview: Part B

Following a pre-screening visit within 10 weeks of day 1 (if applicable), and a 28-day screening period, eligible subjects will be admitted to the clinical unit on the morning of Day -2 (2 days prior to first dosing) for the first inpatient stay. At Day -2, the volunteers will undergo an OGTT, and therefore will need to attend the visit after an overnight fast.

CONFIDENTIAL

Synoptic Clinical Study Protocol
Version 2.0 - 05/08/2017

EudraCT Number: 2017-000380-33

Subjects will receive a single dose of Y14 or placebo by SC injection(s) on Day 1. Subjects will remain in the clinical unit for at least 24 h postdose. It is the intention that subjects will be discharged on Day 4, but they may be discharged on Day 3 after the food intake study has been completed and if the subject is in good health. If volunteers are discharged on Day 3, they will return on Day 4 for collection of a pharmacokinetic sample.

For most of the subsequent inpatient stays (stays 2 to 4) subjects will be admitted to the clinical unit on the day of dosing and will remain in the clinical unit at least until 24 h postdose. In stay 5 the subjects will be admitted to the clinical unit on the day of dosing and will remain in the clinical unit until 48 h postdose. It is proposed that doses will be administered 7 days apart (i.e. on Days 1, 8, 15, 22 and 29).

The proposed duration of the inpatient stays may be altered based on emerging safety, tolerability and PK data from Part A (SAD) or previous cohorts in Part B.

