5.1.5 Discussion of Study Design

This is a double-blinded, randomised, placebo-controlled study in two parts: a single ascending dose study and multiple ascending doses, to investigate the effects of Y14. Note, with the exception of Cohort 1 TP1 which is partially blinded as this will be a crossover design where the volunteers will return for 3 treatment periods. The time interval between each TP should be no less than 1 week. As Y14 is intended as an anti-obesity drug, overweight/obese subjects have been chosen to provide more clinically relevant PK and PD information. With regards to Part B, we propose to recruit patients with Type 2 diabetes or pre-diabetes in order to study the impact of Y14 on glycaemia.

It is the intent of Part B to dose volunteers such that steady-state is achieved and maintained for several days. Based on the available pre-clinical data it is expected that this will be achieved following 28 days once weekly dosing, however, a full review of all the safety, tolerability and pharmacokinetic data from Part A will be performed to confirm the dose regimen for Part B. If

CONFIDENTIAL

the elimination half-life of Y14 is shorter than anticipated from the pre-clinical data, more frequent dosing (e.g. twice weekly) may be appropriate. If the elimination half-life of Y14 is longer than anticipated from the pre-clinical data, dosing every two weeks may be more appropriate (as steady-state will take longer to achieve). The dose frequency will be no more frequent than once a day and no less frequent than once every 14 days. The dosing duration will not exceed 29 consecutive days of dosing.

Details of the dosing regimen and duration used for Part B of the study will be documented in the SMF.

The sample size (approximately 28 subjects in Part A [SAD] and 24 subjects in Part B [MAD]) has been chosen to minimise the number of subjects exposed to Y14 whilst obtaining sufficient information to assess the safety, tolerability, PK and PD of Y14.

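### The Part B dose ceiling is worded three ways, and Section 6.2, read alone, would let individual titration reach a dose that Part A found not tolerated

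*Combined protocol and SAP*

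**What the plan says.** Three statements limit the dose in Part B.

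- Section 5.1.2, on starting Part B: "the total daily dose will not exceed a single dose shown to be safe and well tolerated".
- Section 5.1.2, on the dosing schedule: individual doses "will not exceed the maximal tolerable dose identified from Part A". The next sentence allows titration for an individual subject and does not repeat the limit.
- Section 6.2, on individual titration: "but will not exceed the maximum dose tested in the SAD trial".

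Three further statements concern timing.

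- Section 3.2: "Part B will only commence after appropriate and sufficient data from Part A are available". The stated purpose is to determine a safe starting dose.
- Section 5.1.2: "Part B may commence prior to the completion of Part A". The first ceiling above is the second half of this same sentence.
- Section 5.1.5: "a full review of all the safety, tolerability and pharmacokinetic data from Part A will be performed", in order to confirm the Part B regimen.

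The supplied text does not say how the maximal tolerable dose is identified, or which ceiling prevails if they differ.

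**The concern.** A dose that has been tested is not necessarily one that was tolerated. Both limits in Section 5.1.2 carry a tolerability condition, and the one in Section 6.2 does not. Section 6.2 is the dosing section, and it is the only place where a ceiling is attached to individual titration in the same sentence. A site working from it could titrate a subject to a dose that Section 5.1.2 rules out. The dose a subject receives within a cohort would then depend on which section was followed.

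The protocol's own background makes this matter. Section 3.2 describes the therapeutic window of PYY3-36 as narrow. It also reports that a similar analogue was well tolerated in single doses of 2 to 90 mg, but produced dose-related nausea and vomiting when 90 mg was given repeatedly.

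A second question is whether the ceilings can be applied if Part B starts while Part A is still running.

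**Working it through.** The plan gives no figure to reproduce here. The check compares the three wordings and then applies them to the planned doses.

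**Do the three limits concern the same quantity?** They are phrased for the total daily dose, the individual dose and the titrated dose. Section 5.1.5 allows dosing no more often than once a day, so the total in a day is one dose, even if split into several injections. The limits are directly comparable.

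**Inputs**

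- Planned Part A doses (Section 6.2): 1, 4, 8, 16, 32, 64 and 96 mg, open to modification.
- Escalation rule (Section 3.2): the next level is given only if the previous one was judged safe and well tolerated.
- Assumptions: Part A stops at the first level judged not tolerated, no intermediate dose is added, and the maximal tolerable dose is the level immediately below.

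**Formula.** Let d(i) be the first level not tolerated. It is then the highest dose tested, so the Section 6.2 ceiling is d(i) and both Section 5.1.2 ceilings are d(i−1). The ratio is d(i) / d(i−1).

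| First level not tolerated = Section 6.2 ceiling (mg) | Section 5.1.2 ceilings (mg) | Ratio |
|---|---|---|
| 4 | 1 | 4/1 = 4.0 |
| 8 | 4 | 8/4 = 2.0 |
| 16 | 8 | 16/8 = 2.0 |
| 32 | 16 | 32/16 = 2.0 |
| 64 | 32 | 64/32 = 2.0 |
| 96 | 64 | 96/64 = 1.5 |

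In all six cases the Section 6.2 ceiling equals the dose not tolerated and never lies above it. If every tested level is tolerated, all three ceilings equal the highest dose tested and the ratio is 1.

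**Can the wordings be read together?** Any dose shown to be tolerated has necessarily been tested, so the Section 5.1.2 ceilings can never be higher than the Section 6.2 ceiling. Applied jointly, Section 6.2 adds nothing. Applied separately, it is a looser rule for titration.

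**Early start of Part B**

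| Statement | Usable while Part A is running? |
|---|---|
| Single dose shown to be tolerated (5.1.2) | Yes, once at least one level has been judged tolerated |
| Maximal tolerable dose from Part A (5.1.2) | Possibly not, since it may not have been identified |
| Maximum dose tested (6.2) | Yes, but its value can change as Part A continues, and it carries no tolerability condition |
| Sufficient Part A data before starting (3.2) | Yes, but it concerns the starting dose |
| Full review of all Part A data (5.1.5) | No, not in full until Part A is complete |

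**The case against.** The strongest reply is that the limits are cumulative. Each is an upper bound, and a site satisfies all three by keeping to the tightest. In Section 5.1.2 the sentence allowing titration directly follows the cap at the maximal tolerable dose, and Section 12.2 requires the whole protocol to be read and followed exactly. On that reading, titrating to a dose not tolerated in Part A would breach the protocol. This stands: the conflict arises only if Section 6.2 is read alone. It does not remove the case for correction, because the cumulative reading leaves the Section 6.2 cap without effect and no order of precedence is stated.

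A reader might infer that titration could go above a dose found not tolerated. The documents do not support that. Under Section 3.2, Part A does not escalate past a level that was not judged well tolerated, so the maximum dose tested is at most that level.

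A reader might also infer that an early start leaves Part B without a tolerability limit. That is not supported either. The Section 5.1.2 sentence that permits an early start also sets a tolerability ceiling usable at that time, and Section 3.2 requires sufficient Part A data first.

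Two smaller points stand. The review in Section 5.1.5 serves to confirm the regimen, and the surrounding text is about half-life and dosing frequency, so its conflict with an early start is one of timing rather than of dose ceiling. Escalation can also stop on predicted mean exposure alone (Section 5.1.4), in which case no untolerated dose need have been tested and the ceilings would not diverge. That exposure limit governs escalation by group mean, however, and does not cap an individual subject's titrated dose.

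**Conclusion.** The inconsistency is real but narrower than it may first appear. The Part B ceiling has three wordings, and the one attached directly to individual titration lacks the tolerability condition of the other two. If the highest Part A dose is not tolerated and Section 6.2 is read alone, titration could reach that dose, which Section 5.1.2 forbids.

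The gap would be 1.5-fold to 4-fold on the planned ladder, and zero if every tested dose is tolerated. These ratios are illustrations. They rest on the planned doses, on stopping at the first level not tolerated, and on no intermediate doses. Section 5.1.1 leaves doses open to change and allows additional cohorts, so the actual gap could differ.

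For an early start, two defects remain: the maximal tolerable dose may have no value yet, and a review of all Part A data does not fit with starting before Part A is complete. Because this is a participant-safety limit in a first-in-human trial, the wording should be corrected.

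**What to change.** Reconcile Sections 3.2, 5.1.2, 5.1.5 and 6.2 so that one ceiling, in one wording, governs both cohort doses and individual titration in Part B. State how that ceiling is determined while Part A is still running, including what applies before a maximal tolerable dose has been identified, and how that dose is identified. State which Part A data must have been reviewed before Part B starts, and bring the review described in Section 5.1.5 into line with that. The choice of ceiling belongs to the sponsor and investigator, and this review does not propose one.

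The cost is a change of protocol wording. No change to sample size, assessments or analysis is needed.

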6.3 Treatment Strategy

The clinical staff at Covance Clinical Research Unit, Leeds, are responsible for the ongoing safety and well-being of the volunteers while they are in the clinical unit. There is a paging system to alert the clinical staff to any area in the unit where a subject may need medical attention. In the case of an emergency, cardiac resuscitation trolleys are found in the main ward areas of the clinical unit. These trolleys contain drugs, equipment for airway insertion, circulation lines, defibrillation etc, together with oxygen cylinders and portable suction machines. There is a physician on-call 24 hours a day (this can be off site) and all physicians are Advanced Life Support (ALS) trained. In addition, the clinical staff can contact further on-call physicians or public emergency services, including the ambulance service, in the event of

CONFIDENTIAL

Synoptic Clinical Study Protocol
Version 2.0 - 05/08/2017

EudraCT Number: 2017-000380-33

a serious medical event. Equipment and emergency drugs are available to treat common medical emergencies that might occur in a Phase I study.

6.4 Warnings and Precautions

As this is the first administration of Y14 to man, all effects cannot be reliably predicted. The preclinical data suggest an acceptable safety margin. Facilities and staff for resuscitation and the treatment of other medical emergencies will be provided.

6.5 Prior and Concomitant Medication

The participants are not allowed to take any prescription medication within 2 weeks of first dosing apart from those required for treatment of their diabetes, hypercholesterolaemia and hypertension. Subjects are not allowed to take any non-prescription medication (excluding paracetamol) or megadose (intake of 20 to 600 times the recommended daily dose) vitamins within 7 days of first dosing prior to entrance into the clinical research facility and for the duration of the study.

In the interests of subject safety and acceptable standards of medical care the Investigator will be permitted to prescribe treatment(s) at his/her discretion. All treatments must be recorded in the subjects' case report form (CRF) (medication, dose, treatment duration and indication).

